10.4 Exploratory Efficacy Endpoint

10.4.1 Additional Quality of Life Analyses

EQ-5D-5L

The EQ-5D-5L has five dimensions: mobility, self-care, usual activities, pain/discomfort and anxiety/depression. These dimensions are measured on a five level scale: no problems, slight problems, moderate problems, severe problems, and extreme problems.

The scores for the 5 dimensions are used to compute a single utility index score ranging from zero (0.0) to 1 (1.0) representing the general health status of the individual. The EQ-5D-5L also contains a visual analog scale (VAS) to assess the subject's overall health.

Additional exploratory analyses comparing the effects of venetoclax + cytarabine versus placebo + LDAC will be performed on the following PRO measures: EQ-5D-5L, and the subscales/items from the EORTC QLQ-C30 and PROMIS Cancer Fatigue SF 7a. Scores will be calculated as per the scoring manuals for all scales/items of the EORTC QLQ-C30, PROMIS Cancer Fatigue SF 7a, the EQ-5D-5L utility score, and the EQ-5D VAS score at each assessment. Linear mixed effects regression models similar to that described in Section 10.3.7 will be used to test for differences between treatment arms. Within-group changes from baseline and between-group comparisons at each assessment will also be assessed. Additional analyses may include an assessment of time to deterioration and time to improvement.

10.4.2 Duration of CR + CRi

Duration of CR + CRi will be defined as the number of days from the date of first response (CR or CRi) per the modified IWG criteria for AML to the earliest evidence of confirmed morphologic relapse, progressive disease or death due to disease progression. If a subject is still responding at the data cutoff date, then the subject will be censored. The disease assessment data after the onset of any post-treatment therapy will not be included in the duration of CR + CRi analysis. The detailed censoring rule is described in Table 5. Duration of CR + CRi will be analyzed for all randomized subjects who achieve the best response of CR or CRi.

Table 5. Event/Censor and Corresponding Event/Censor Time for Duration of CR + CRi

Situation	Event/Censor	Event Time/Censor Time
Confirmed morphologic relapse (MR)* or progressive disease (PD) on or prior to any post-treatment therapy and data cutoff date, whichever is earliest	Event	Earliest MR or PD event date
Death due to disease progression on or prior to data cutoff date regardless whether it occurred after any post-treatment therapy initiated	Event	Death date
No confirmed MR, * PD, or death due to disease progression events and without post-treatment therapy initiated on or prior to the data cutoff date	Censor	Last disease assessment date (bone marrow or hematology lab collection date) on or prior to the data cutoff date
No confirmed MR, * or PD on or prior to post-treatment therapy initiated on or prior to the data cutoff date, no death due to disease progression on or prior to data cutoff date	Censor	Start date of post-treatment therapy

* An un-confirmed MR is defined as a MR with bone marrow blast $\leq 10\%$ and followed by non-PD/Non-MR prior to the post-treatment therapy. Otherwise, MR is considered to be a confirmed MR.

The distribution of duration of CR + CRi will be estimated for each treatment arm using Kaplan-Meier methodology. Median duration of CR + CRi will be calculated and 95% confidence interval for median duration of CR + CRi will be presented by treatment arm.

Analysis of modified duration of CR + CRi that includes death from all causes by the cutoff date will be performed as a sensitivity analysis.

10.4.3 Duration of CR

Duration of CR will be defined as the number of days from the date of first CR per the modified IWG criteria for AML to the earliest evidence of morphologic relapse, progressive disease, or death due to disease progression. The censoring rule described in [Table 5](#) will be applied to the analysis of duration of CR.

Analysis of modified duration of CR that includes death from all causes by the cutoff date will be performed as a sensitivity analysis.

10.4.4 Duration of CR + CRh

Duration of CR + CRh will be defined as the number of days from the date of first response (CR or CRh) to the earliest evidence of morphologic relapse, progressive disease or death due to disease progression. The censoring rule described in [Table 5](#) will be applied to the analysis of duration of CR + CRh.

Analysis of modified duration of CR + CRh that includes death from all causes by the cutoff date will be performed as a sensitivity analysis.

10.5 Efficacy Analysis per Independent Review Committee

An Independent Review Committee (IRC) will evaluate disease assessment data on all randomized subjects. The analysis for the following efficacy endpoints, described in [Section 10.3](#) and [Section 10.3.8](#), will be conducted based on this IRC review:

- CR rate
- CR + CRi rate
- CR + CRi rate by the initiation of Cycle 2
- EFS

10.6 Additional Efficacy Analysis

In addition to the stratified log-rank test for the primary and secondary efficacy endpoints, the following analyses may be performed for the comparison of OS, CR rate, CR + CRi rate, CR + CRh rate, CR + CRi rate by the initiation of Cycle 2, and CR + CRh rate by the initiation of Cycle 2 between the two treatment groups.

- Un-stratified log-rank test and the Cox proportional hazards model for OS
- CMH test for CR rate and CR + CRi rate using IRC data
- Fisher's exact test for CR rate and CR + CRi rate using investigator assessment data and IRC data

- Modified analyses for OS, CR rate, CR + CRi rate, CR + CRi rate by the initiation of Cycle 2, CR + CRh rate, and CR + CRh rate by the initiation of Cycle 2 to use all data available in the extracted database (no "Cutoff" date).

10.7 Handling of Multiplicity

The fixed sequence testing procedure will be performed with a significance level of 0.05 for the primary endpoint OS and key secondary efficacy endpoints sequentially. If statistical test is not significant for the primary efficacy endpoint of OS, then statistical significance will not be declared for any of the secondary efficacy endpoints. The Lan-DeMets alpha spending function with O'Brien-Fleming boundary will be used at the interim and final analysis to ensure that the false positive rate for each primary or key secondary efficacy endpoint is 0.05 or less.

For CR + CRi rate, CR + CRi rate by the initiation of Cycle 2, CR + CRh rate, CR + CRh rate by the initiation of Cycle 2, CR rate, transfusion independence rates, and MRD response rate, the information fraction to be used at IA (100 death events) is calculated as detailed in [Table 6](#).

Table 6. Calculation of Information Fraction (IF)

Endpoint	Information Fraction
CR + CRi rate	Portion of subjects with at least 6 months follow up since randomization
CR + CRh rate	Portion of subjects with at least 6 months follow up since randomization
MRD response rate	Portion of subjects with at least 6 months follow up since randomization
CR + CRi rate by the initiation of Cycle 2	Portion of subjects who started Cycle 2 Day 1 dosing or discontinued treatment by the end of Cycle 1
CR + CRh rate by the initiation of Cycle 2	Portion of subjects who started Cycle 2 Day 1 dosing or discontinued treatment by the end of Cycle 1
CR rate	Portion of subjects with at least 9 months follow up since randomization
Transfusion independence rates (RBC/Platelet)	Portion of subjects with at least 9 months follow up since randomization

Table 7 (for EU and EU reference countries) and Table 8 (for US and US reference countries) present the hierarchical ranking and alpha spending for each ranked primary and secondary endpoints at IA and FA.

Table 7. Alpha-spending Boundary (One-sided p-value) for Each Ranked Endpoint for EU and EU Reference Countries

Endpoint		Timing of Analysis	
		IA	FA
1	OS	As specified in Table 2	As specified in Table 2
2	CR + CRi rate ^a	To be calculated with IF as specified in Table 6	To be calculated with IF as specified in Table 6
3	Post-baseline platelet transfusion independence ^a	To be calculated with IF as specified in Table 6	To be calculated with IF as specified in Table 6
4	CR + CRi rate in IDH1/2 subgroup ^{a,b}	To be calculated with IF as specified in Table 6	To be calculated with IF as specified in Table 6
5	CR rate ^a	To be calculated with IF as specified in Table 6	To be calculated with IF as specified in Table 6
6	CR + CRi by the initiation of Cycle 2 ^a	To be calculated with IF as specified in Table 6	To be calculated with IF as specified in Table 6
7	Post-baseline RBC transfusion independence ^a	To be calculated with IF as specified in Table 6	To be calculated with IF as specified in Table 6
8	MRD and CR + CRi response rate ^a	To be calculated with IF as specified in Table 6	To be calculated with IF as specified in Table 6
9	EORTC QLQ-C30	0.0001	0.025
10	PROMIS Cancer Fatigue SF 7a	0.0001	0.025
11	OS in IDH1/2 subgroup ^b	0.0001	0.025
12	OS in FLT3 subgroup ^b	0.0001	0.025
13	CR + CRi rate in FLT3 subgroup ^b	0.0001	0.025
14	EFS	0.0001	0.025

- a. The Lan DeMets with O'Brien-Fleming approach will be applied to determine the efficacy boundaries of the following ranked secondary endpoints with the information fraction define in Table 6.
- b. If the size of identified subgroup population is less than 30 or randomization ratio between Venetoclax + LDAC arm and placebo + LDAC arm is higher than 3:1 at the time of IA and FA, the endpoint will be ranked below EFS in the fixed sequence testing procedure.

Table 8. Alpha-spending Boundary (One-sided p-value) for Each Ranked Endpoint for US and US Reference Countries

Endpoint		Timing of Analysis	
		IA	FA
1	OS	As specified in Table 2	As specified in Table 2
2	CR + CRh rate ^a	To be calculated with IF as specified in Table 6	To be calculated with IF as specified in Table 6
3.	CR + CRi rate ^a	To be calculated with IF as specified in Table 6	To be calculated with IF as specified in Table 6
4	Post-baseline platelet transfusion independence ^a	To be calculated with IF as specified in Table 6	To be calculated with IF as specified in Table 6
5	CR + CRh rate in IDH1/2 subgroup ^{a,b}	To be calculated with IF as specified in Table 6	To be calculated with IF as specified in Table 6
6	CR rate ^a	To be calculated with IF as specified in Table 6	To be calculated with IF as specified in Table 6
7	CR + CRh by the initiation of Cycle 2 ^a	To be calculated with IF as specified in Table 6	To be calculated with IF as specified in Table 6
8	Post-baseline RBC transfusion independence ^a	To be calculated with IF as specified in Table 6	To be calculated with IF as specified in Table 6
9	MRD and CR + CRh response rate ^a	To be calculated with IF as specified in Table 6	To be calculated with IF as specified in Table 6
10	MRD and CR + CRi response rate ^a	To be calculated with IF as specified in Table 6	To be calculated with IF as specified in Table 6
11	PROMIS Cancer Fatigue SF 7a	0.0001	0.025
12	EORTC QLQ-C30	0.0001	0.025
13	OS in IDH1/2 subgroup ^b	0.0001	0.025
14	OS in FLT3 subgroup ^b	0.0001	0.025
15	CR + CRh rate in FLT3 subgroup ^b	0.0001	0.025
16	EFS	0.0001	0.025

- a. The Lan DeMets with O'Brien-Fleming approach will be applied to determine the efficacy boundaries of the following ranked secondary endpoints with the information fraction define in Table 6.
- b. If the size of identified subgroup population is less than 30 or randomization ratio between Ven + LDAC arm and placebo + LDAC arm is higher than 3:1 at the time of IA and FA, the endpoint will be ranked below EFS in the fixed sequence testing procedure.

10.8 Efficacy Subgroup Analyses

To evaluate the impact of demographic and baseline characteristics on efficacy, subgroup analyses will be performed, but not limited to, for CR rate, CR + CRi rate, CR + CRh rate, CR + CRi rate by the initiation of Cycle 2, CR + CRh rate by the initiation of Cycle 2, and overall survival. The subgroups in the full analysis set including, but not limited to, those defined below will be used for these analyses:

1. Gender (Male, Female)
2. Age (18 – < 65 years, 65 – < 75 years, ≥ 75 years)
3. AML status (de novo, secondary)
4. Type of secondary AML (therapy related, post MDS/CMML)
5. Region (US, EU, China, JP, ROW)
6. Baseline ECOG (< 2, ≥ 2)
7. Subjects who received prior HMA for MDS (Yes, No)
8. Cytogenetic risk categorization (Favorable, Intermediate, Poor)
9. Molecular marker (FLT3, IDH1/2, TP53, NPM1)
10. AML with Myelodysplasia related changes (AML-MRC)

11.0 Safety Analysis

Safety assessments will only include subjects in the safety analysis set as described in Section 5.1. Safety will be assessed by treatment received for the safety analysis set.

11.1 Analysis of Treatment-Emergent Adverse Events

All summaries/analyses involving AEs will include treatment-emergent adverse events (TEAE) only, unless otherwise specified. TEAEs are defined as any adverse event with onset after the first dose of study drug and no more than 30 days after the last dose of

study drug. Events where the onset date is the same as the study drug start date are assumed to be treatment-emergent. If an incomplete or missing onset date was collected for an AE, the AE will be assumed to be treatment-emergent unless there is evidence that confirms that the AE was not treatment-emergent (e.g., the AE end date was prior to the date of the first dose of study drug).

For summaries of AEs related (reasonable possibility) to study drug, at each level of summation (overall, SOC, and PT) each subject is counted only once. If a subject has an AE with unknown relationship, then the subject will be counted in the relationship category of "unknown," even if the subject has another occurrence of the same event with a relationship of "no reasonable possibility" present. The only exception is if the subject has another occurrence of the same AE with the relationship of "reasonable possibility." In this case, the subject will be counted under the reasonable possibility category.

Adverse event data will be summarized and presented using primary MedDRA system organ classes (SOCs) and preferred terms (PTs) according to the MedDRA coding dictionary version 21.0 or higher.

The number and percentage of subjects experiencing treatment-emergent adverse events will be summarized for the following adverse event summaries:

- Any treatment-emergent adverse event.
- Any treatment-emergent adverse event with NCI toxicity (CTCAE V4.03) grade 3, 4, or 5 adverse events.
- Any treatment-emergent serious adverse event.
- Any treatment-emergent adverse event with reasonable possibility related to venetoclax/placebo by the investigator.
- Any treatment-emergent adverse event leading to discontinuation of venetoclax/placebo.
- Any treatment-emergent adverse event leading to venetoclax/placebo interruption.

- Any treatment-emergent adverse event leading to venetoclax/placebo reduction.
- Any treatment-emergent adverse event with reasonable possibility related to LDAC by the investigator.
- Any treatment-emergent adverse event leading to discontinuation of LDAC.
- Any treatment-emergent adverse event leading to LDAC interruption.
- Any treatment-emergent adverse event leading to LDAC reduction.
- Any treatment-emergent adverse event leading to death.

In addition, the treatment emergent AEs and serious AEs for selected grouped preferred terms (PTs) including, but not limited to, those listed in [Table 9](#), will be summarized.

Table 9. Selected Adverse Events

Selected Adverse Events	Search Criteria
Tumor Lysis Syndrome (AE)	SMQ – "Tumor Lysis Syndrome" (narrow)
Grade \geq 3 neutropenia	PT terms – "neutropenia," "neutrophil count decreased," "febrile neutropenia," "agranulocytosis," "neutropenic infection," and "neutropenic sepsis"
Grade \geq 3 infection, including opportunistic infections	SOC of "infections and infestations"
Haemorrhages	SMQ – "Haemorrhages" (narrow)
Anemia	PT terms – "Anaemia" and "Haemoglobin decreased"
Thrombocytopenia	PT terms – "Thrombocytopenia" and "Platelet count decreased"

There will be no statistical comparison for TEAEs between two treatment arms.

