6.1.3 Relationship to Study Drug

The investigator will use the following definitions to assess the relationship of the adverse event to the use of study drug:

- Reasonable Possibility** After consideration of factors including timing of the event, biologic plausibility, clinical judgement, and potential alternative causes, there is **sufficient** evidence (information) to suggest a causal relationship.
- No Reasonable Possibility** After consideration of factors including timing of the event, biologic plausibility, clinical judgement, and potential alternative causes, there is **insufficient** evidence (information) to suggest a causal relationship.

The Investigator will assess the relationship of each adverse event to venetoclax/placebo, and to LDAC. Some events may be reasonably related to more than one drug or to none. For causality assessments, events assessed as having a reasonable possibility of being related to the study drug will be considered "associated." Events assessed as having no reasonable possibility of being related to study drug will be considered "not associated." In addition, when the Investigator has not reported causality or deemed it not assessable, AbbVie will consider the event associated to study drug.

If an Investigator's opinion of no reasonable possibility of being related to study drug is given, an "Other" cause of event must be provided by the Investigator for the serious adverse event.

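### SAP 11.1 sets events of unknown causality apart while Protocol 6.1.3 counts them as associated, so related-event counts can fall below the protocol's own rule

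*SAP*

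**What the plan says.** **Protocol 6.1.3 (Relationship to Study Drug)** defines two causality ratings, *reasonable possibility* and *no reasonable possibility*, and calls them associated and not associated. The rating is made per drug: "The Investigator will assess the relationship of each adverse event to venetoclax/placebo, and to LDAC". There is no third rating. The section covers gaps with a default: "when the Investigator has not reported causality or deemed it not assessable, AbbVie will consider the event associated to study drug".

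**SAP 11.1 (Analysis of Treatment-Emergent Adverse Events)** sets the counting rule for summaries of related events. Within these, "at each level of summation (overall, SOC, and PT) each subject is counted only once". It then adds a third category: "If a subject has an AE with unknown relationship, then the subject will be counted in the relationship category of" unknown. That category takes precedence over *no reasonable possibility*. It gives way only when the same event also occurred with a rating of *reasonable possibility*.

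Two rows in the SAP 11.1 list depend on this rule: "Any treatment-emergent adverse event with reasonable possibility related to venetoclax/placebo by the investigator" and "Any treatment-emergent adverse event with reasonable possibility related to LDAC by the investigator".

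**The concern.** The two documents give different answers for the same record. If causality is left blank or is rated impossible to assess, the protocol treats the event as associated, while the SAP leaves the subject out of the related rows. The SAP does not mention the protocol default, say that it is departing from it, or give a reason.

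The SAP handles another kind of missing data in the same section the opposite way. An event with a missing or partial onset date is presumed treatment-emergent unless there is evidence against it. Missing causality gets no such presumption, although the protocol supplies one.

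At stake is whether the related-event tables agree with the protocol's causality rule and with case assessments made under it. Where they disagree, the tables show fewer related events.

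**Working it through.** The plan states no figure on this point, so there is nothing to reproduce. The check compares the two rules and then works out what one affected subject is worth.

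**Inputs**
- Protocol rule: Protocol 6.1.3.
- SAP rule, its one exception, and one count per subject per level: SAP 11.1.
- Planned arm sizes of 140 and 70: Protocol 8.2 and SAP 4.3.

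**Step 1. Every combination of ratings.** For one event and one drug, a subject's occurrences can carry any non-empty mix of three ratings: related (R), not related (N) and unknown (U). That gives 2³ − 1 = 7 mixes.

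| Ratings present | SAP 11.1 | Protocol 6.1.3 | Same? |
|---|---|---|---|
| N | not related | not associated | yes |
| R | related | associated | yes |
| N, R | related | associated | yes |
| U, R | related | associated | yes |
| U, N, R | related | associated | yes |
| U | unknown | associated | **no** |
| U, N | unknown | associated | **no** |

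Two of the seven mixes differ, and both differ in the same direction.

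**Step 2. Direction.** Let u be the number of subjects at a given level with at least one unknown rating and no related rating. Then

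related count under the protocol rule − related count under the SAP rule = u ≥ 0.

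The SAP count can equal the protocol count or fall below it. It cannot exceed it.

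**Step 3. Size per subject.** The difference in percentage points is 100 × u / n.

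| u (assumed) | n = 140 | n = 70 |
|---|---|---|
| 0 | 0 | 0 |
| 1 | 0.71 | 1.43 |
| 2 | 1.43 | 2.86 |
| 5 | 3.57 | 7.14 |

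The values of u are illustrations, not estimates. Neither document says how many events had unknown causality.

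**Step 4. Which rows move.** The overall row changes only for a subject who has no related event of any kind. Such a subject also changes the organ-class and preferred-term rows for that event. The reverse does not hold: a subject with an unknown event in one organ class and a related event in another changes the lower rows but not the overall one. The lower-level rows are therefore the more exposed.

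**Step 5. Is it reconciled elsewhere?** Protocol 8.1.7.2 asks for events by relationship to study drug but gives no rule for missing causality. The SAP is written to Amendment 4, and the current amendment's summary of changes (Protocol 1.1) does not list Section 6.1.3, so a change of version does not explain the difference.

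**The case against.** **The rows report investigators; the default belongs to the sponsor.** Both related rows in SAP 11.1 are labelled as the investigator's attribution, while Protocol 6.1.3 says what the sponsor will do when the investigator has given none. A table of what investigators recorded does not by itself contradict a sponsor default. This has force, and any fix must respect it by relabelling. It does not remove the point: the SAP never says that these rows are meant to exclude the default, and no other row in its list applies it.

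**The subjects are not hidden.** They sit in a category of their own rather than being folded into not related, and the SAP lets unknown override *no reasonable possibility*. A reader could add the two categories if both are tabulated. This stands, and a claim that events are lost would go too far. But the related rows are the ones listed, and the SAP does not say that an unknown row will be shown beside them.

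**The consequence is small.** SAP 11.1 plans no statistical comparison of treatment-emergent events. The summaries of all, grade 3 to 5, serious and fatal events, the grouped terms in SAP Table 9, and the deaths in SAP 11.2 do not depend on causality. This stands in full and sets the weight of the point.

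Stronger readings that a reader might infer are not supported:
- *That the related counts are in fact too low, by an amount that can be estimated.* No count or rate of unknown causality is given. With a two-way scale for investigators there may be none. Results of other venetoclax studies described in the protocol do not help, because it reports no unknown-causality events for them.
- *That unknown ratings gather in the events hardest to separate from leukaemia.* Protocol 6.1.7 says that the cause of some events seen under LDAC in another trial is uncertain. It does not say that investigators here leave such events unrated.
- *That the rule favours venetoclax.* It is the same in both arms, and the venetoclax/placebo assignment is blinded until after the final analysis. The documents do not show which way the difference between arms would move.

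**Conclusion.** The conflict is real and its direction is certain; its size is not known. Whenever an event of unknown causality is a subject's only potentially related one at a given level, the SAP's related-event count is lower than the protocol's rule would give. Both differing combinations of ratings go that way, and none goes the other.

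The conclusion rests on three assumptions:
- Unknown in the SAP covers what the protocol describes as unreported or not assessable. The SAP does not define the term.
- The SAP's exception, worded for repeats of the same event, is taken at organ-class and overall level to cover any related event within that level.
- The denominators are the planned randomised numbers. The safety set contains only subjects who took at least one dose, so its denominators, and hence the value of one subject, may differ slightly.

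This is a minor safety-reporting correction. Efficacy, alpha and sample size are unaffected.

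**What to change.** In SAP 11.1:
1. State that missing, unknown or not-assessable causality is counted as *reasonable possibility* in the related-event summaries, separately for venetoclax/placebo and for LDAC, in line with Protocol 6.1.3.
2. Replace the sentences that give unknown its own category.
3. Relabel the two related rows so that they are not described as purely the investigator's attribution, for example as related by investigator rating or by protocol default.
4. Footnote, for each arm and drug, the number of subjects assigned by default, so that the investigator-only count can still be recovered.

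The cost is a few lines of SAP text, a short change to the derivation code, and one footnote. Where such events exist, related-event percentages rise slightly. Protocol 1.1 says that the final analysis has been completed, so for tables already produced the same end is met by re-running the related-event tables or by adding the footnoted counts.
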